#### **4.2.3 Secondary endpoint:** Targeted AEs reported post cryotherapy (Arm A)

Table: Listing of targeted AEs with number (%) of arm A subjects with the AE

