The medical history must **document any history of genital condyloma; any AIDS-defining illness or condition as defined by the Centers for Disease Control and Prevention; any history of cervical, vaginal, or vulvar LSIL or HSIL on cytology or histology; and menstrual history. The medical history must also include all diagnoses identified by the ACTG criteria for clinical events and other diagnoses within 45 days prior to study entry.** For current criteria, refer to the appendix identified in the study CRF. Any allergies to any medications and their formulations **should be documented in the source documents only.**

2. Language in three subsections of Section 6.3.6, "Clinical Assessments," has been changed.

- a. Subsection "Signs/Symptoms" now reads:

At entry, all signs and symptoms Grade ≥ 3 that occurred within 45 days prior to entry must be recorded **on the CRF.**

Post entry, signs and symptoms Grade ≥ 3 must be recorded **on the CRF.**

In addition, post entry, all grades of signs and symptoms related to cervical cryotherapy or LEEP treatments that are contained within the DAIDS "Female Genital Grading Table for Use in Microbicide Studies" will be captured (<http://rsc.tech-res.com/safetyandpharmacovigilance/>). **Grade 1 or 2 signs and symptoms should be recorded on study-specific CRFs only. Grade ≥ 3 should be recorded on study-specific CRFs as well as on the generic event CRFs.**

- b. Subsection "Diagnoses" now reads:

After entry, record any new diagnoses made since the last visit using the ACTG criteria for clinical events and other diseases.

Except for invasive cancer, cervical cytology and histology results do not need to be recorded as events; these results will be entered on study-specific CRFs only.

- c. Subsection "Concomitant Medications" now reads:

Concomitant Medications

Record ART medications (including start and stop dates) **and** receipt of HPV vaccines, and receipt of medical or surgical treatment for ~~genital warts, vulvar intraepithelial neoplasia (VIN) or vaginal intraepithelial neoplasia (VAIN)~~. Any antibiotics, hormonal treatment, or prescribed or over-the-counter treatments for gynecological conditions should be recorded.

These updates will be included in the next version of the A5282 protocol if it is amended.

Letter of Amendment #2 for:

A5282

A Randomized, Phase II Trial to Compare an HPV Test-and-Treat Strategy to a Cytology-based Strategy for Prevention of CIN 2+ in HIV-infected Women

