6.3 Instructions for Evaluations

All clinical and laboratory information required by this protocol is to be present in the source documents. Sites must refer to the Source Document Guidelines on the DAIDS web site for information about what must be included in the source document:

<http://www.niaid.nih.gov/labsandresources/resources/daidsclinsrch/documents/sourcedocappndx.pdf>.

All stated evaluations are to be recorded on the CRF and entered into the ACTG database unless otherwise specified. This includes events that meet the International Conference on Harmonisation (ICH) definitions for a serious adverse event:

- Results in death
- Life-threatening
- Requires inpatient hospitalization or prolongation of existing hospitalization
- Results in persistent or significant disability/in capacity
- Congenital anomaly/birth defect
- Other important medical event (may not be immediately life-threatening or result in death or hospitalization but may jeopardize the patient or may require intervention to prevent one of the events listed above).

To grade diagnoses, signs and symptoms, and laboratory results, sites must refer to the DAIDS Table for Grading the Severity of Adult and Pediatric Adverse Events (DAIDS AE Grading Table), Version 1.0, December 2004 (Clarification, August 2009) and Addendum 1-Female Genital Grading Table for Use in Microbicide Studies, which can be found on the DAIDS RSC web site: <http://rsc.tech-res.com/safetyandpharmacovigilance/>.

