6.3.6 Clinical Assessments

Targeted Physical Examination

Post entry, a targeted physical examination is to include vital signs (temperature, pulse, and blood pressure) and is to be driven by any previously identified or new signs or symptoms including diagnoses that the participant has experienced since the previous visit.

Signs and Symptoms

At entry, all signs and symptoms Grade ≥ 3 that occurred within 45 days prior to entry must be recorded; post entry, signs and symptoms Grade ≥ 3 must be recorded. Post entry, all grades of signs and symptoms related to cervical cryotherapy or LEEP treatments that are contained within the DAIDS "Female Genital Grading Table for Use in Microbicide Studies" will be captured (<http://rsc.tech-res.com/safetyandpharmacovigilance/>).

Diagnoses

Record all diagnoses identified by the ACTG criteria for clinical events and other diseases.

Concomitant Medications

Record ART medications (including start and stop dates), receipt of HPV vaccines, and receipt of medical or surgical treatment for genital warts, vulvar intraepithelial neoplasia (VIN) or vaginal intraepithelial neoplasia (VAIN). Any antibiotics, hormonal treatment, or prescribed or over-the-counter treatments for gynecological conditions should be recorded.

Adherence Assessment

The site should discuss and encourage ongoing adherence to ART at each study visit if the participant is receiving ART. Any concerns about adherence should be communicated to the participant's primary care provider. This should be documented in the source documents only.

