6.3.7 Laboratory Evaluations

At screening, entry, and post entry record all Grade ≥ 3 laboratory values.

Hematology

ANC, platelet count, and HgB.

Pregnancy Test

For women with reproductive potential, a negative serum or urine β -HCG (urine test must have a sensitivity of <25 mIU/mL) pregnancy test must be performed within 48 hours prior to study entry, prior to cryotherapy and LEEP (if done), and post entry whenever pregnancy is suspected. (See section 7.4 for the management of study participants who become pregnant after entry.)

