#### 4.1.5 Baseline Summaries

- Baseline demographics, sociodemographic and health variables: age, race/ethnicity, IV drug use history, ART use, CD4 count, nadir CD4 count, highest level of education complete, average annual household income, number of children
- Baseline sexual history: age of first vaginal sex, total number of vaginal sex partners
- Baseline cytology and Abbott hr-HPV results

**4.2 Primary Endpoint:** CIN2+ (CIN2, CIN3 or invasive cancer) by biopsy 26 weeks post randomization through 130 weeks post randomization, as determined by local review at a DAIDS-assessed laboratory

Note: LEEP outcome prior to week 16 will be considered baseline evaluation and will not be used as an endpoint.

Tables (ITT and per-protocol): cumulative rates of arm A and arm B subjects who developed CIN2+ from week 26 to week 130; one-sided 95% upper CI for arm B proportion minus arm A proportion.

SDAC validation: The calculation of time to CIN2+ and the one-sided 95% upper CI will be double-programmed.

In addition, (to evaluate design assumptions and precursory design assumptions,) the following will be reported:

- Arm A and Arm B: CIN2+ rate from week 26 to week 130
- Arm A and Arm B: week 0 invasive cancer
- Arm B: number (%) diagnosed with CIN2+ at baseline
- Arm B: number (%) with CIN2+ at baseline who were successfully treated before week 26. Note that we only have a limited number of participants with cervical (non-LEEP) biopsy results before week 26.
- number (%) of subjects with abnormal pap smear and CIN2+ at baseline
- number (%) of subjects with CIN2+ at baseline who were successfully treated before week 26.

**4.2.1 Secondary endpoint:** Time to CIN2+ diagnosis by biopsy, as determined by local review at a DAIDS-assessed laboratory

Figures (ITT and per-protocol): survival curves with p-value from stratified log-rank test comparing arms A and B.

Figure: For Arm A, survival curves with p-value from log-rank test comparing participants with and without hr-HPV at week 26 based on: (a) aHPV, and (b) Xpert

Figure: For Arm A, survival curves with p-value from log-rank test comparing participants with and without cervical cytologic abnormalities at week 26.

Figures (ITT): survival curves with p-value from stratified log-rank test comparing arms A and B.

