#### **4.2.4 Secondary endpoint:** Targeted AEs reported post LEEP

Table: Listing of targeted AEs with number (%) of subjects with the AE

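### The planned final analysis gives no between-arm estimate of harm, although Grade 3 or higher and serious events are recorded in both randomised arms

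*SAP*

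**What the plan says.** **What is collected.** Protocol 6.3.6, as revised by Clarification Memo #1, says "Post entry, signs and symptoms Grade ≥ 3 must be recorded on the CRF" and "After entry, record any new diagnoses made since the last visit using the ACTG criteria for clinical events and other diseases". Protocol 6.3.7 says "At screening, entry, and post entry record all Grade ≥ 3 laboratory values". Protocol 6.3 sends the required evaluations to the CRF and database, and adds "This includes events that meet the International Conference on Harmonisation (ICH) definitions for a serious adverse event". None of these is limited to one arm. The Schedule of Events (6.1) places clinical assessments at entry and at weeks 26, 52, 78, 104 and 130.

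**What is analysed.** SAP 2.3 marks the safety and tolerability of cryotherapy as an objective that this plan addresses. Two adverse-event tables follow:

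- SAP 4.2.3, after cryotherapy: "Table: Listing of targeted AEs with number (%) of arm A subjects with the AE".
- SAP 4.2.4, after LEEP: "Table: Listing of targeted AEs with number (%) of subjects with the AE". No split by arm is stated.

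The other items that touch on harm are a listing of deaths (SAP 4.1.3), the line "Arm A and Arm B: week 0 invasive cancer" (SAP 4.2), and a comparison of discontinuation by Fisher's exact and log-rank tests, with reasons listed (SAP 4.2.6). Protocol 9.6.2.1 and 9.6.2.2 plan the same two procedure-based descriptions of targeted events. Protocol 9.5 has the DSMB review cryotherapy-related events and overall reported events in the study arms.

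**The concern.** Randomisation is between strategies, not procedures. Each strategy brings its own mix of biopsies, cryotherapy and LEEP, so the relevant harm question is how many women in each arm had a serious or severe event over 130 weeks. A table confined to Arm A has no comparator. A post-LEEP table that is not split by arm cannot show which strategy led to the LEEP and its complications.

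The protocol's rationale describes test-and-treat as safe as well as effective. If the final report gives a randomised contrast for CIN2+ and none for severe or serious events, its balance of benefit and harm is one-sided, even though the data for the other side are on the CRFs.

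**Working it through.** **Step 1. Set collection beside analysis.**

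| Data recorded after entry in both arms | SAP table or listing |
|---|---|
| Grade 3+ signs and symptoms (6.3.6, Clarification Memo #1) | None by arm; procedure-related ones may appear in the targeted tables |
| New diagnoses (same) | None by arm |
| Serious events (6.3) | Deaths listed only (SAP 4.1.3) |
| Grade 3+ laboratory values (6.3.7) | None |
| Signs and symptoms below Grade 3, captured only if related to cryotherapy or LEEP | Targeted tables (SAP 4.2.3, 4.2.4) |

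The first four rows support a randomised comparison. Haematology is scheduled at screening only, so post-entry laboratory data will be sparse. The last row does not support one. Below Grade 3, a symptom is captured only when tied to cryotherapy or LEEP, and after entry the targeted assessment is scheduled only 4 weeks after treatment.

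**Step 2. How LEEP exposure should differ by arm.** Inputs from Protocol 9.4: 24% with CIN2+ at first colposcopy, cytology sensitivity 80%, treatment efficacy 90%, event rates from week 26 to week 130 of 20% (Arm B) and 6% (Arm A), and 140 women per arm.

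- The plan's own figure: 0.24 × 0.80 × 0.90 = 0.173, against the stated 17%. It reproduces.
- Arm B, CIN2+ found at the entry work-up: 0.24 × 0.80 × 140 = 26.9, about 27 women.
- Arm B, CIN2+ from week 26 on: 0.20 × 140 = 28.
- Arm A, CIN2+ from week 26 on: 0.06 × 140 = 8.4, about 8.

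These are diagnoses, not procedures performed. Some Arm B women may be counted twice, and treatment after a previous LEEP is discretionary. The direction is still clear: most randomised women with LEEP should be in Arm B, while nearly all cryotherapy is in Arm A.

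**Step 3. Precision of a by-arm comparison.** The documents give no adverse-event rates, so 2%, 5% and 10% in both arms are assumptions. Half-width of the 95% interval = 1.96 × √(2p(1 − p)/n). With n = 140, and with n = 112 (140 less the planned 20% loss):

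| Assumed rate | n = 140 | n = 112 | Rate in other arm detectable with 80% power, two-sided 5%, n = 140 |
|---|---|---|---|
| 2% | ±3.3 points | ±3.7 | 9.9% |
| 5% | ±5.1 points | ±5.7 | 15.1% |
| 10% | ±7.0 points | ±7.9 | 22.3% |

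At 2% there would be about 3 events per arm (0.02 × 140 = 2.8), too few for the normal approximation to be reliable. With no events in 140 women, the exact upper limit of the two-sided 95% interval is 1 − 0.025^(1/140) = 2.6%.

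**Step 4. Invasive cancer.** Cancer on the Arm A pre-cryotherapy biopsy is a primary failure (Letter of Amendment #1). Week 0 cancer is reported for both arms (SAP 4.2), and cancer from week 26 on falls within CIN2+ and CIN3+. Two gaps remain. One is a cervical cancer found after the baseline work-up and cleared by week 26. The other is vaginal and vulvar cancer, which needs expedited reporting (Protocol 11.4.2) but has no SAP table.

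**The case against.** The strongest reply is that the SAP does what the protocol asks. The safety objective concerns cryotherapy in Arm A (Protocol 1.3.1), the safety endpoints are targeted events after each procedure (9.2.2), and 9.6.2 only describes them. The trial is a proof of concept that is not powered for secondary objectives, and the SAP presents itself as a proposed outline of key analyses. All of this stands. The gap begins in the protocol, and a reader who inferred that the SAP departs from it would be wrong.

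Three other stronger readings are tempting, and the documents do not support them:

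- *Harm is never compared or reported by arm.* The DSMB reviews overall events in the study arms, procedure-related Grade 3 and 4 serious events are reported in an expedited manner, and discontinuation is compared. What is missing is an estimate in the planned analyses.
- *Arm B is an unused control for background pelvic symptoms or bleeding.* It is not one below Grade 3. Arm B women without LEEP have no targeted assessment visit after entry, and their milder symptoms are not captured.
- *Planned exposure is about 140 cryotherapies against 27 LEEPs.* That omits LEEP after CIN2+ found from week 26 on, as Step 2 shows.

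Nor does SAP 4.2.4 say that the arms will be pooled. It is silent on a split.

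**Conclusion.** The point holds for the planned analyses. Followed as written, they give no randomised estimate for severe events, serious events or cancer at all anatomical sites, although these are recorded in both arms. The primary test, sample size and conduct are unaffected.

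The added comparison would be descriptive. Its half-width is about 3 to 7 points at assumed rates of 2% to 10% with 140 per arm, and about 4 to 8 points with 112. It could rule out a large excess of harm but not a small one: at 5% in one arm, the other would need to reach about 15% for 80% power. The comparison also assumes that Grade 3 or higher and serious events are recorded equally well in both arms. The study is open label and the 4-week post-treatment visit is an extra contact, so this should be stated as a limitation. This is a cheap improvement, not an error in the plan.

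**What to change.** Add to the SAP one descriptive intention-to-treat table by randomised arm, from randomisation to week 130. Give the number and percentage of women with:

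- (a) any Grade 3 or higher event;
- (b) any serious event, including death;
- (c) invasive cervical, vaginal or vulvar cancer at any time.

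Show for each the Arm A minus Arm B risk difference with a two-sided 95% interval, by an exact or score method if events are few.

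Split the post-LEEP targeted-event table by arm, with the number of women who had LEEP in each arm as the denominator. Keep the post-cryotherapy table. Present procedure-related targeted events by arm as counts of strategy burden only, with a note that they are ascertained only around procedures, so Arm B does not control for background rates.

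The cost is one new table and one added column split, from CRFs already completed. No new data, visits or sample size are needed. The downside is wide intervals for rare events.

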#### **4.2.4 Secondary endpoint:** Targeted AEs reported post LEEP

Table: Listing of targeted AEs with number (%) of subjects with the AE

#### **4.2.5 Secondary endpoint:** Cervical cytology results at study visits

Table (based on arms A and B): Cytology results (normal, abnormal:LSIL, abnormal:HSIL) at study visits with p-value from Fisher's test.

Table (based on arm A only): (Crosstabulation of) Cytology results at baseline and week 26 with p-value from McNemar's test.

Tables (based on arms A and B cytology results after study entry): Results of longitudinal logistic mixed effects models with independent variables nadir CD4 count, baseline/screening characteristics (e.g., HIV RNA level, current CD4 count, sexual history and cytology outcome) and recent sexual activity (time-updated variables on number of vaginal sex partners and frequency of condom use within the previous 6 months) **[EXPLORATORY]**

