9.3 Randomization and Stratification

The participants with hr-HPV by aHPV, and for whom cryotherapy is appropriate, will be randomized with equal probability to Arm A or B to receive immediate cryotherapy at study entry (Arm A) or to follow the cytology-based strategy (Arm B). Randomization to Arms A and B will be stratified by the current use of ART (any ART or no ART). There will also be institutional balancing to help ensure roughly equal sizes of Arms A and B at a given site. Enrollment will continue until the study has accrued at least 140 participants in each of Arms A and B. Approximately 170 participants will be enrolled in Arm C. There is no required minimum number of participants to be enrolled in Arm C. Randomization will be by permuted blocks with institutional balancing.

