9.4 Sample Size and Accrual

For the primary analysis, cumulative occurrence of CIN2+ on biopsy from week 26 to week 130 will be compared between Arms A and B.

The study reported by Kuhn et al [22] implies about a 43% cumulative rate of CIN2+ among women infected with HIV at entry in the delayed evaluation arm compared to about 7% in the HPV test-and-treat arm (comparable to Arm A) for HIV-infected and hr-HPV positive women with 3-year follow-up. However, unlike the delayed evaluation arm in Kuhn's study, some of the women in Arm B in the current study may be diagnosed with CIN2+ based on the abnormal baseline cervical cytology that leads to colposcopy and possibly successful treatment within 26 weeks. Hence, the CIN2+ rate in Arm B is likely to be less than 43% approximated from the delayed evaluation arm in Kuhn's study. It is approximated that 24% of the hr-HPV-positive, HIV-infected women will be diagnosed with CIN2+ at the first colposcopy, based on the baseline HPV prevalence and the month 6 colposcopy results reported by Kuhn et al [22]. Assuming that the sensitivity of cervical cytology is approximately 80% and the efficacy of the treatment is 90%, it is approximated that 17% of the HPV-infected women in Arm B will be diagnosed with CIN2+ and treated successfully prior to week 26. Taking into account that these CIN2+ events will not count as events in the A5282 study, using an assumed exponential distribution for time to event to adjust for the shorter follow up time in A5282 compared to the Kuhn study, and using the three year cumulative event rates of 7% and 43% in the Kuhn study's HPV-and-treat arm and delayed evaluation arm, respectively, we estimate the cumulative CIN2+ event rate from week 26 to week 130 in Arm A and Arm B to be about 6% and 20%, respectively.

As a proof-of-concept study, the protocol team plans to conduct a one-sided test using time-to-event methods that adjust for interval censored data at a type 1 error rate of 5% to show improvement with immediate cryotherapy (Arm A) with at least 90% power. Assuming a 20% rate in Arm B and 6% rate in Arm A leads to a study sample size of 111 in each arm. Table 2 below presents a conservative estimate [42] of the power to detect various rate differences between the study arms with the sample size of 111 in

each arm using a Fischer's exact test. Based on simulations, the actual analysis method will have at least as much power as presented in Table 2.

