9.6.2 Analyses of Secondary Endpoints

Secondary objectives will be evaluated with 2-sided tests or 2-sided confidence intervals with a significance level of 5%. The study is not powered to test the secondary study objectives formally, and no adjustment will be made to the type I error rates to account for multiple testing.

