#### **4.2.6 Secondary endpoint:** Early study discontinuation rates and reasons (arms A and B)

Table: Number (%) subjects who discontinued; p-value from Fisher's exact test.

Table/Listing: For subjects who discontinued study prematurely, the following will be listed: off study week, reason for early study discontinuation.

Figure: KM plot of time to discontinuation with p-value from log-rank test. The time to study discontinuation will be the number of weeks between off-study date and randomization date.

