#### 4.2.7 Secondary endpoint: aHPV results (detected, not detected) after study entry

Table (based on arms A and B): hr-HPV aHPV results at study visits after entry with p-value from Fisher's test.

Tables (based on arms A and B): Results of longitudinal logistic mixed effects models with independent variables nadir CD4 count, baseline/screening characteristics (e.g., HIV RNA level, current CD4 count, sexual history and cytology outcome) and recent sexual activity (time-updated variables on number of vaginal sex partners and frequency of condom use within the previous 6 months) **[EXPLORATORY]**

NOTE: In case of limited aHPV results, Fisher's/logistic will only be done at select weeks.

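### The 2x2 Fisher tests for discontinuation and aHPV run at about 3-4% instead of 5%, and these analyses leave out the ART stratum used elsewhere

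*SAP*

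**What the plan says.** Protocol 9.3: "Randomization to Arms A and B will be stratified by the current use of ART (any ART or no ART"). The stratum is then used where the main endpoint is analysed. SAP section 3 weights the Arm B minus Arm A difference in CIN2+ over baseline ART use, and SAP 4.2.1 and 4.2.2 call the between-arm log-rank tests for CIN2+ and CIN3+ stratified.

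Three other between-arm comparisons use Fisher's test with no stratum:

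- SAP 4.2.6, discontinuation: "Number (%) subjects who discontinued; p-value from Fisher's exact test". The accompanying log-rank test for time to discontinuation is named without the word stratified.
- SAP 4.2.7, a detected/not detected outcome: "hr-HPV aHPV results at study visits after entry with p-value from Fisher's test".
- SAP 4.2.5, cytology in three categories (normal, LSIL, HSIL): "at study visits with p-value from Fisher's test".

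Protocol 9.6.2.1 has the same Fisher tests and plain log-rank, so the SAP does not depart from it. Protocol 9.6.2 calls for "2-sided tests or 2-sided confidence intervals with a significance level of 5" per cent, and adds: "The study is not powered to test the secondary study objectives formally".

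**The concern.** A test announced at 5% should run close to 5%. Fisher's test conditions on both margins, and on a 2x2 table the conditional distribution is so coarse that the attained level often falls well short of nominal. Leaving out a prognostic stratification factor can lower it further. The result is a weaker test with no compensating gain.

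The endpoint where this matters most is discontinuation (objective 1.3.3). The sample size in protocol 9.4 assumes that loss to follow-up is unrelated to the endpoint. A non-significant comparison of dropout may be read as reassurance, so a conservative test does not protect anyone there. The plan also asks for only a p-value from these Fisher comparisons, with no estimate of the difference and no interval.

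**Working it through.** **Inputs from the documents.** Two-sided 5% for secondary tests (protocol 9.6.2); 1:1 allocation (9.3); 140 enrolled per arm, up to 20% loss, 111 evaluable per arm required (9.4). Discontinuation is assessed on everyone enrolled to Arms A and B (SAP section 3), so n = 140 per arm. For aHPV at a visit I use 140 x 0.8 = 112 up to 140.

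**Assumptions.** The documents give no event rates for these endpoints, no ART share and no ART effect. Ranges are shown instead.

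**Step 1: the plan's own figure.** Protocol 9.4 says "Assuming a 20% rate in Arm B and 6% rate in Arm A leads to a study sample size of 111 in each arm", for a one-sided test "at a type 1 error rate of 5% to show improvement with immediate cryotherapy (Arm A) with at least 90% power". With mean rate 0.13 and difference d = 0.14:

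- Uncorrected n' = [1.645 x sqrt(2 x 0.13 x 0.87) + 1.282 x sqrt(0.20 x 0.80 + 0.06 x 0.94)]^2 / 0.14^2 = 96.95, so 97.
- Fisher-type correction: n = (n'/4) x [1 + sqrt(1 + 4/(n' x d))]^2 = (96.95/4) x (2.138)^2 = 110.8, so 111.

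This reproduces the plan (power 90.1%; all nine cells of Table 2 agree within 1 point). It also shows that the protocol already recognises a price for Fisher's test: 111 - 97 = 14 women per arm in the design calculation.

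**Step 2: true level of the 2x2 tests.** For x events in one arm and y in the other, the Fisher p-value sums the hypergeometric probabilities of all tables no more likely than the one observed. The level at common rate p is the sum over all (x, y) of Bin(x; n, p) x Bin(y; n, p) where that p-value is at most 0.05. The comparator is the one-table Mantel-Haenszel chi-square, which has no strata and so isolates discreteness.

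| Common rate | Fisher, 112 per arm | Chi-square, 112 | Fisher, 140 per arm | Chi-square, 140 |
|---|---|---|---|---|
| 10% | 2.8% | 5.2% | 3.2% | 4.8% |
| 20% | 3.4% | 5.0% | 3.5% | 5.0% |
| 40% | 3.5% | 4.8% | 3.7% | 4.9% |
| 50% | 3.8% | 5.2% | 3.6% | 4.8% |

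At common rates of 3-5%, Fisher's level is 1.3-2.3%.

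**Step 3: power by the same enumeration.**

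| Rates | n per arm | Fisher | Chi-square | Loss (points) |
|---|---|---|---|---|
| 20% vs 10% | 140 | 59.4% | 65.9% | 6.5 |
| 20% vs 8% | 140 | 79.5% | 84.0% | 4.5 |
| 20% vs 6% | 140 | 93.1% | 95.1% | 2.0 |
| 40% vs 25% | 112 | 62.6% | 67.3% | 4.7 |
| 20% vs 10% | 112 | 48.7% | 55.7% | 7.0 |

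Over a wider set of rates at 111 and 140 per arm, the loss is 2.0-9.3 points against the (Pearson) chi-square. By simulation against the ART-stratified Cochran-Mantel-Haenszel (CMH) test, with an odds ratio of 0.45, it is 3.0-9.8 points. The CMH level in these runs is 4.7-5.2%.

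**Step 4: how much is due to ART?** CMH statistic: [sum over k of (a_k - n_Ak x t_k/N_k)]^2 / sum over k of [n_Ak x n_Bk x t_k x (N_k - t_k) / (N_k^2 x (N_k - 1))], where k is the ART stratum, a_k the Arm A events and t_k the total events.

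- ART not prognostic: Fisher 3.4-3.8%, unstratified chi-square 4.8-5.1%. The shortfall is there without any ART effect.
- ART moderately prognostic (15 points between strata, 60/40 split, 112 per arm): unstratified chi-square against CMH power is 73.9% vs 74.0% in one scenario and 67.0% vs 68.4% in another. Fisher has about 69% and 62%. Most of the gap is between Fisher and chi-square.
- ART strongly prognostic (25% vs 60%): unstratified chi-square falls to 3.4-4.3% and Fisher to 2.4-3.0%. Here stratification matters in its own right.

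**Step 5: the cytology table.** SAP 4.2.5 is a 2x3 table, for which the exact test is far less coarse. In simulations with 8,000 replicates (standard error about 0.24 points at a 5% level), its level was 4.7-5.2% against 4.6-5.3% for chi-square. Power loss was 0.2-0.4 points, for example 58.7% against 59.1% at 111 per arm for 60/30/10% vs 75/20/5%.

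**The case against.** The case for leaving the plan alone is respectable. Fisher's test never exceeds its nominal level, so no false-positive rate is inflated. The protocol itself names these tests, declares the secondary objectives not powered and makes no multiplicity adjustment. For aHPV and cytology it also plans longitudinal mixed models that compare the arms, so the visit-wise tests are not the only evidence. The size of the power loss rests on assumed rates. All of this stands, and it keeps the point minor. It answers least for discontinuation, which has no such model.

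Two stronger readings are tempting and not supported.

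- A reader might infer that every Fisher test in the SAP runs near 3%, cytology included. Step 5 shows otherwise: the three-category test is near nominal. The 2x2 figures would apply only if cytology were collapsed to normal against abnormal, which is not what SAP 4.2.5 sets out.
- A reader might infer that the shortfall arises because ART is ignored. Step 4 shows that it is mainly discreteness. Protocol 2.1 does report ART as an independent predictor of CIN severity at one site (adjusted odds ratio 2.16), which makes the stratum worth using. It does not establish a strong effect on discontinuation or on aHPV after entry.

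Nor is the missing stratum general among the between-arm log-rank tests: it concerns only time to discontinuation. No level or power was computed for that test; the argument there is consistency with the randomisation.

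**Conclusion.** The point holds for SAP 4.2.6 and 4.2.7. Their 2x2 Fisher tests have a true two-sided level of about 3-4% for common rates of 10-50%, lower for rarer events, against the stated 5%. The cost is roughly 2-10 points of power, with assumed event rates and 111-140 women per arm. Discreteness is the main cause; leaving out ART adds a material loss only if ART is strongly prognostic, which the documents do not settle. The three-category test in SAP 4.2.5 is sound in level as written. This is a cheap improvement to secondary analyses and not an error that threatens a conclusion: it is conservative, and the primary analysis is unaffected.

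**What to change.** - SAP 4.2.6 and 4.2.7: replace Fisher with the CMH test stratified by the ART stratum used at randomisation. Report the stratified risk difference with a two-sided 95% confidence interval. Keep an exact test where expected counts are small (say, any expected cell below 5).
- SAP 4.2.6: stratify the time-to-discontinuation log-rank by ART.
- SAP 4.2.5: keep the three-category table. Since objective 1.3.2 concerns the presence of abnormality, add an ART-stratified abnormal-versus-normal comparison as a further line, and say that it is an addition.
- Record that these choices replace the tests named in protocol 9.6.2.1, or give a reason for keeping them.

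The cost is a few sentences in the SAP and a small program change. The ART stratum is already needed for the primary analysis, so no new data are required.
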